### **9.3 Definition of Populations**

Our population includes patients 18-65 years old who have tested positive with COVID-19 and are either asymptomatic but exposed in the prior 10 days, or are symptomatic with symptom development in the prior 10 days. Inclusion and exclusion criteria (described elsewhere) will be met. We are not treating patients for their COVID-19 infection.

### **9.4 Interim Analyses and Stopping Rules**

An interim analysis will be conducted after 120 patients are enrolled and samples collected; block randomization will be planned to randomize in batches of 120 participants, with 20 randomized to each mouthrinse. Therefore, we can do an interim analysis with an  $n=120$ . This sample size is sufficient to determine antiviral efficacy at 30 minutes post-mouthrinse. If mouthrinses are ineffective at reducing viral infectivity at timepoints 15 and 30 minutes, then that mouth rinse arm will be discontinued for further enrollment and will be removed from the block randomization calendar, with initiation of a subsequent trial with fewer arms. This will allow us to enroll sufficient numbers of patients to statistically evaluate longer time point efficacy for the mouthrinses with antiviral efficacy (the longer time points require larger samples sizes for sufficient statistical power).

If no mouthrinse has antiviral effects at this interim analysis point, the study will be stopped due to lack of efficacy. Because all oral rinse products are commercially available, low risk products that have previously undergone extensive safety testing and approval procedures, we do not anticipate a situation where safety concerns to participants necessitates halting the study. Adverse events will be reported and reviewed by our internal quality control committee. Medical problems that occur in our facility will be reported as needed to the IRB board and emergency medical personnel will be contacted to care for the patient and potentially bring them to the adjacent UNC medical hospital. If a significant number of adverse events or reactions are witnessed (defined as more than 1 per every 20 patients), a safety review will be triggered and study personnel will look at the records in an unblinded fashion to see if one mouthrinse is causing reactions. If that is the case, the mouthrinse study arm associated with adverse events will

be discontinued, but the mouthrinse arms associated with minimal adverse events will continue.

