After the participant expectorates the mouth rinse, research staff will collect another salivary sample (T0, 2 mL over 5 minutes). During a 10 minute recuperation period, the study participants will answer demographics survey questions and questions regarding the taste, color, flavor and general acceptability of using the mouthrinse as part of routine dental and medical visits. Patients will be asked to smell an ammonia ampule (“smelling salts”) to evaluate sense of smell, as loss of olfaction is indicative of the acute infection phase. At 15 minutes post-rinse, the participant will be asked to provide an additional saliva sample (2 mL over 5 minutes), followed by another 10 minute recuperation period. This sequence will be repeated for at the 30, 45 and 60 minute time points post rinse. At 60 minutes, the study participant will give their final salivary sample (2 mL over 5 min), and study participation will conclude.

All salivary samples will be collected on ice in sterile 15 mL conical vials labelled “COVID Core” and using pre-printed labels including patient’s random alphanumeric study ID. Saliva samples will be cataloged and stored at the UNC Delta COVID Translational Initiative (also known as the Covid-19 Core) for future qRT-PCR, viral infectivity, and rapid antigen or sandwich ELISA assays. Samples will be transported on ice from the collection site to 4403A Koury Hall in leak proof biohazard bags. Samples will be processed according to the **sample processing and outcomes** procedure (below).

Following study participation completion, participants will receive \$50 compensation in the form of a Visa gift card.

During the period that the COVID+ study participants are present in the clinic and giving saliva samples, we will monitor oxygen saturation and inquire about their comfort. If participants exhibit signs of distress or if oxygen saturation drops, research study staff will contact emergency medical responders (present in the building) to visit the patient and if deemed appropriate, the participants will be escorted to UNC hospital (adjacent building).

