#### **Sample Size Considerations**

Based on similar viral infectivity studies evaluating antiviral mouth rinse efficacy, we were able to run power calculations to estimate effect size and determine sample size as a function of length of mouthrinse time course. The sample size is justified by a paired t-test on outcomes between time points. With three simultaneous comparisons (T1-T0, T2-T1, and T2-T0 = 30 minute time course), the sample size n=6 can detect the effect size in Cohen's  $d=0.7$ , which is between medium and large, over 80% power and 0.016 type-I error rate by Bonferroni correction. With six simultaneous comparisons (T1-T0, T2-T1, T2-T0, T3-T0, T3-T2, T3-T1) = 45 minute time course, the sample size n=53 can detect the effect size in Cohen's  $d=0.7$ , which is between medium and large, over 80% power and 0.016 type-I error rate by Bonferroni correction. With ten simultaneous comparisons (T1-T0, T2-T1, T2-T0, T3-T0, T3-T2, T3-T1, T4-T3, T4-T2, T4-T1, T4-T0) = 60 minute time course, the sample size n=78 can detect the effect size in Cohen's  $d=0.7$ , which is between medium and large, over 80% power and 0.016 type-I error rate by Bonferroni correction.

Statistical analysis of our data will be performed by [name], the statistician on this project.

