## **9.2 Sample Size and Randomization**

Based on similar viral infectivity studies evaluating antiviral mouth rinse efficacy, we were able to run power calculations to estimate effect size and determine sample size as a function of length of mouthrinse time course. The sample size is justified by a paired t-test on outcomes between time points. With three simultaneous comparisons (T1-T0, T2-T1, and T2-T0 = 30 minute time course), the sample size n=6 can detect the effect size in Cohen's d =0.7, which is between medium and large, under 80% power and 0.016 type-I error rate by Bonferroni correction. With six simultaneous comparisons (T1-T0, T2-T1, T2-T0, T3-T0, T3-T2, T3-T1) = 45 minute time course, the sample size n=53 can detect the effect size in Cohen's d =0.7, which is between medium and large, under 80% power and 0.016 type-I error rate by Bonferroni correction. With ten simultaneous comparisons (T1-T0, T2-T1, T2-T0, T3-T0, T3-T2, T3-T1, T4-T3, T4-T2, T4-T1, T4-T0) = 60 minute time course, the sample size n=78 can detect the effect size in Cohen's d =0.7, which is between medium and large, under 80% power and 0.016 type-I error rate by Bonferroni correction.

[name], who is the statistical consultant on this project, will create a block randomization schedule and perform these computations. All patients will be consented and then fill out our screening questions for inclusion and exclusion to confirm eligibility prior to being assigned to the randomization schedule.

The researcher responsible for collecting the salivary samples will be blinded to the mouthwash solution, as they will be given a pre-aliquoted mouthrinse in an unlabeled storage syringe to provide to the patient for the rinse. The syringe will be opaque to mask any coloring of the solution.

The PI, Co-I, study coordinators and study personnel who work for GoHealth are authorized to break the blinding if a patient suffers an allergic or adverse reaction to one of the mouthrinses. Though highly unlikely as all mouthrinses are sold commercially at Walgreens and CVS, adverse or allergic reactions are possible. Using the numerical code associated with the participant and mouthrinse syringe, the study personnel can reference the block randomization schedule to determine the mouthrinse type, to inform the emergency medical workers, poison control or the emergency room what type of mouthrinse product led to the reaction.

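### Section 9.4's claim that 20 per arm suffices at 30 minutes rests on a wrong figure: n=6 gives 12.7% power, 20 gives 68% at 0.016, and the drop rule has no criterion

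*Combined protocol and SAP*

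**What the plan says.** Section 9.4 plans to "randomize in batches of 120 participants, with 20 randomized to each mouthrinse" and to analyse the first batch. It calls this number adequate at 30 minutes ("This sample size is sufficient to determine antiviral efficacy at 30 minutes post-mouthrinse") and attaches two decisions to the result:

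- Dropping an arm: "If mouthrinses are ineffective at reducing viral infectivity at timepoints 15 and 30 minutes, then that mouth rinse arm will be discontinued". The arm is then "removed from the block randomization calendar, with initiation of a subsequent trial with fewer arms".
- Stopping the trial: "If no mouthrinse has antiviral effects at this interim analysis point, the study will be stopped due to lack of efficacy".

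Section 9.4 gives no test, alpha, comparator or size of reduction for either decision.

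The only 30-minute calculation is under Sample Size Considerations in 9.1, repeated in 9.2: "and T2-T0 = 30 minute time course), the sample size n=6 can detect the effect size", with d=0.7, 80% power and a Bonferroni alpha of 0.016 for three comparisons (T1-T0, T2-T1, T2-T0). Section 9.2 adds: "The sample size is justified by a paired t-test on outcomes between time points". P values are two-tailed (9.1, Primary Outcomes).

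The sample labelled T0 comes after the rinse. Section 3 says: "After the participant expectorates the mouth rinse, research staff will collect another salivary sample", and Section 5.1 calls it time 0. The planned infectivity analyses do use the pre-rinse value: the reduction factor (9.1 Tertiary Outcomes, 9.6) and the log-scale ANCOVA (9.6).

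**The concern.** The interim rule removes arms and can end the trial, so its sample size needs a calculation that holds. The figure it appears to lean on, n=6 for d=0.7 at alpha 0.016, is implausibly small for a paired t-test. If it is wrong, nothing in the plan shows what 20 per arm can detect.

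Two further gaps affect the same decision. First, the three powered contrasts compare post-rinse samples with each other. A rinse that works at once and keeps working would show T1-T0 and T2-T0 near zero, so these contrasts do not measure the effect the rule asks about. Second, with no comparator, alpha or threshold, the same data could keep or drop an arm depending on choices made after the results are seen. The two infectivity targets elsewhere in the plan do not agree, so neither can be assumed to define ineffective.

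**Working it through.** **Inputs.** Paired t-test, d=0.7, alpha 0.016, 80% power, n=6 (9.1, 9.2); two-sided (9.1); 20 per arm (9.4). I read d as the mean paired difference over its own SD; the documents do not say.

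**1. The plan's own figure.** Power = P(|T| > t(1-alpha/2; n-1)), where T is noncentral t with n-1 degrees of freedom and noncentrality d√n.

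| n | d√n | critical t at 0.016 | power at 0.016 | power at 0.05 |
|---|---|---|---|---|
| 6 | 0.7 × 2.449 = 1.715 | 3.573 | 12.7% | 28.7% |
| 20 | 0.7 × 4.472 = 3.130 | 2.644 | 68.5% | 84% |
| 25 | 0.7 × 5 = 3.500 | 2.592 | 81% | 92% |

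The stated n=6 is not reproduced. The smallest n for 80% is 25 at 0.016 (19 at 0.05). The effect detectable with 80% power at 0.016 is d=1.89 for n=6 and d=0.79 for n=20.

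**2. Other readings of n=6.** One-sided 0.016 gives 21%; one-sided 0.05 gives 43%. If d is on the raw-SD scale, the paired effect is d/√(2(1-ρ)); even with ρ=0.9, n=6 gives 62%. None reaches 80%.

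**3. Other readings of n=20.** One-sided 0.016 gives 78.6%. With d on the raw-SD scale, power at two-sided 0.016 is 36%, 68% and 95% for ρ = 0, 0.5 and 0.75.

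**4. Chance of failing the drop rule.** The single-test miss rate at n=20 is 1 - 0.685 = 32% at 0.016 and 1 - 0.844 = 16% at 0.05. The rule, however, names both 15 and 30 minutes. I simulated 20 pairs with true d=0.7 at both times and an assumed correlation between the two changes:

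| Correlation | both non-significant, 0.016 | both non-significant, 0.05 |
|---|---|---|
| 0.3 | 13% | 4% |
| 0.9 | 25% | 11% |

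**5. The two infectivity targets.** >50% is log10(2) = 0.30 log10; >95% is log10(20) = 1.30 log10. The documents give no SD for the log10 change. Assuming 1.0, 1.5 or 2.0, a true 1.30 log10 change gives d = 1.30, 0.87 or 0.65 and, with 20 pairs at 0.016, power of 99.8%, 88% or 61%. A true 0.30 log10 change with SD 1.0 gives d=0.30, noncentrality 0.30 × 4.472 = 1.34, and power of about 12%. Which target applies decides whether 20 is enough.

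**6. If arms are judged against saline, 20 v 20, carrying d=0.7 over (an assumption).** Unadjusted t-test: noncentrality 0.7√10 = 2.214, 38 degrees of freedom, power 39% at 0.016 (58% at 0.05). For ANCOVA with the pre-rinse covariate (37 degrees of freedom, equal pre and post variances assumed), the result depends on the scale of d:

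- d in SD units of the change: effective d = 0.7/√((1+r)/2) = 0.868 at r=0.3 and 0.738 at r=0.8; power at 0.016 is 59% and 43%.
- d in raw-SD units: effective d = 0.7/√(1-r²) = 0.734 and 1.167; power is 43% and 87%.

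The defensible range is about 43-87%.

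**The case against.** - **Twenty exceeds six, so Section 9.4 follows from the stated calculation.** True, and the error sits upstream in 9.1 and 9.2. But once n=6 falls, nothing else supports the claim. If n=6 is a typing error for a figure near 25, then 20 still falls short at 0.016.
- **Twenty may be enough.** At an unadjusted 0.05 it gives 84%, and for a >95% reduction it gives 88% or more if the SD is 1.5 log10 or less. This stands: a reader might infer that 20 per arm is inadequate, and the documents do not support that. They support only that adequacy has not been shown.
- **The wrongful-drop risk is below the single-test miss rate.** This also stands. A reader might infer that about one in three effective rinses would be dropped at 0.016. The natural reading of the rule requires failure at both times, which gives 13-25%. The trial stops only if every rinse fails, which is rarer still if several work.
- **Saline is safe.** A reader might infer that the rule would drop the control, because the Précis and 5.3.1 count six rinses including 0.9% NaCl and nothing exempts it. That is strained: Section 3 calls the trial placebo-controlled and labels NaCl the control, and the hypotheses concern antiseptic rinses. A clarifying line is enough.
- **The comparator is specified elsewhere.** Partly. Sections 9.1 and 9.6 plan before-after reduction factors, comparisons between rinses and ANCOVA, but 9.4 does not say that its rule uses them.

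**Conclusion.** The concern holds in this form. The n=6 figure is wrong on every reading tried, and the sufficiency statement in 9.4 is left without support at the plan's own alpha: 68% power for d=0.7, against the 80% planned. The powered contrasts do not match the planned infectivity analysis, and the drop rule cannot be applied as written because its comparator, alpha and threshold are missing and the plan's two infectivity targets differ by 1.00 log10.

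The consequence is moderate: roughly a 13-25% chance at 0.016, or 4-11% at 0.05, that a rinse with a true d of 0.7 at both times fails both tests. This rests on d as a standardised paired difference, within-arm paired testing, non-significance being taken as ineffectiveness, and the assumed correlation of 0.3-0.9.

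The correction is needed before the interim analysis because the rule is decisive and Section 9.5 has the evaluating committee unmasked to assignment.

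**What to change.** 1. In 9.1 and 9.2, correct n=6 to 25 for the stated inputs, or state the power that n=6 gives. Define the contrasts against the pre-rinse sample.
2. In 9.4, replace the sufficiency sentence with the power of 20 per arm at a stated alpha (68% at 0.016 or 84% at 0.05, paired, d=0.7). State that non-significance alone does not establish ineffectiveness.
3. Reconcile the >50% target (9.1) with the >95% target (1.2 and 9.5.2), and cite the reconciled figure in the drop rule.
4. As a clarification, say that the drop rule applies to the five experimental rinses and that the NaCl control stays in later blocks. Tie the rule to the log-scale analysis with the pre-rinse value and the comparison between rinses already planned in 9.6.

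The cost is protocol wording, with no extra patients or samples. Item 4 has a price: an unadjusted comparison with saline at 20 v 20 has 39% power at 0.016, against 68% within arm. ANCOVA power should be reported as a range (about 43-87%), because the scale of d and the pre-post correlation are undocumented. Item 4 therefore needs item 2 beside it, and a weak rinse may stay in longer.

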### **Sample Size and Population**

We will enroll 80 outpatient COVID+ subjects per mouth rinse, with 6 mouth rinses, requiring us to enroll 480 COVID+ patients. Patients will be randomized to their mouthrinse. These patients will have already had a confirmed COVID+ test prior to enrollment. There will be no stratification to our randomization. In addition to having a COVID+ test, patients will need to be at least 18 years of age and at most 65 years of age and in good oral health without any known allergies or reactions to commercial

dental products, mouthrinses or iodine. Patients who are pregnant, nursing/lactating, who have a cognitive or developmental disability, who are taking lithium, who have or have ever had a thyroid problem, who have kidney dysfunction, who have an active oral herpes flare up, who have any oral viral infection and/or flare up, who have significant mucosal tears, growths or damage to their mouth, who have uncontrolled severe periodontal disease with bleeding gums, and those who have xerostomia will be excluded from the study. There is no exclusion criteria based on gender or race.

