### 9.5.1 Primary Outcomes

The primary objectives of this study are to determine the efficacy of antiseptic mouthwashes on reducing SARS-CoV-2 viral RNA and protein antigen levels in COVID+ patient saliva. *We hypothesize that COVID-19+ patients will have a >95% reduction in SARS-CoV-2 viral RNA and protein antigen levels following a 60 second oral rinse with an antiseptic mouthrinse and that this reduction will persist for at least 30 minutes.* These primary objectives will assess SARS-CoV-2 viral load based on viral RNA measured by quantitative real time PCR and viral protein antigen levels measured by rapid antigen or sandwich ELISA assays. These objectives provides urgently needed data to guide healthcare workers on the proper use of specific commercially available

mouthwashes capable of reducing SARS-CoV-2 in saliva and potentially limiting COVID-19+ transmission.

Outcome assessments will be conducted weeks to months after the study visit, when qRT-PCR and sandwich ELISA or rapid antigen assays are conducted in the COVID core and the [name] lab.

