### 9.5.2 Tertiary Outcomes

The first tertiary objective will focus on quantifying SARS-CoV-2 viral infectivity using an *in vitro* infectivity assay. *We hypothesize that COVID-19+ patients will have a >95% reduction in SARS-CoV-2 viral infectivity following a 60 second oral rinse with an antiseptic mouthrinse and that this reduction will persist for at least 30 minutes.* This objective provides urgently needed data to guide healthcare workers on the proper use of specific commercially available mouthwashes capable of reducing SARS-CoV-2 viral infectivity and potentially limiting COVID-19+ transmission. Our second tertiary objective is to determine the **feasibility** and **acceptability** of using antiseptic mouthwashes by patients in healthcare settings. *We hypothesize that patients will welcome the use of commercially available antiseptic mouthrinses into clinical practice.* Patients enrolled in the randomized mouthrinse study will be surveyed on the taste, appearance, sensation, and acceptability of using the mouthrinse in healthcare settings. Understanding acceptability of a mouthrinse protocol is critical to implementation and therefore the ability to reduce COVID-19 transmission risk in clinical settings.

Outcome assessments will be conducted weeks to months after the study visit, when viral infectivity assays are conducted in the COVID core and the [name] lab.

Survey results will be evaluated using bivariate, descriptive statistics and non-parametric methods as appropriate for the question type. Outcome assessments will be conducted weeks to months after the study visit, when statistical analyses are conducted.

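### Section 9.4 drops a rinse arm at the interim on infectivity alone, a tertiary outcome, so a rinse active on the primary outcomes can be closed at about 20 of 80 patients with its primary comparison underpowered

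*Combined protocol and SAP*

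**What the plan says.** The ranking of outcomes is consistent across the document. Section 9.5.1 states: "The primary objectives of this study are to determine the efficacy of antiseptic mouthwashes on reducing SARS-CoV-2 viral RNA and protein antigen levels". Section 1.1 and the statistical hypothesis in section 9.1 agree, and both set a horizon of at least 30 minutes. Section 9.5.2 places infectivity lower: "The first tertiary objective will focus on quantifying SARS-CoV-2 viral infectivity using" an in vitro assay. Section 1.2 agrees.

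Planned enrolment is in the Précis: "We will enroll 80 outpatient COVID+ subjects per mouth rinse, with 6 mouth rinses, requiring us to enroll 480 COVID+ patients". Section 9.4 sets the interim at 120 patients: "block randomization will be planned to randomize in batches of 120 participants, with 20 randomized to each mouthrinse". It then gives two efficacy rules in different terms:

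- For an arm: "If mouthrinses are ineffective at reducing viral infectivity at timepoints 15 and 30 minutes, then that mouth rinse arm will be discontinued".
- For the whole study: "If no mouthrinse has antiviral effects at this interim analysis point, the study will be stopped due to lack of efficacy".

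The arm rule names infectivity and nothing else. The whole-study rule does not name an outcome. Neither rule has a threshold, test or alpha. Section 9.4 also says of the interim number: "This sample size is sufficient to determine antiviral efficacy at 30 minutes post-mouthrinse".

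**The concern.** An interim rule for lack of efficacy should act on what the trial is mainly meant to establish, or the plan should explain why it acts on something else. Here a tertiary outcome decides which arms stop enrolling, and nothing exempts an arm that is working on RNA or antigen. The document does not explain or reconcile this.

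Assay timing does not account for it. Section 9.5 gives the same turnaround of weeks to months for qRT-PCR, antigen and infectivity. Section 3 plans these assays on the same stored saliva. RNA or antigen data could be produced for the same 120 patients.

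At stake is the precision of the primary comparison for any rinse closed this way. It would also lose most of its RNA and antigen data at 45 and 60 minutes, and section 9.4 itself says the later time points need larger samples.

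**Working it through.** **1. The interim count.** 120 patients / 6 rinses = 20 per rinse, as the plan states. Planned size is 480 / 6 = 80.

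**2. The plan's claim that the interim number suffices at 30 minutes.** Section 9.2 gives n = 6 for the 30-minute course, from a paired t-test with d = 0.7, 80% power and alpha 0.016. Section 9.6 makes P values two-tailed. With the exact noncentral t (noncentrality d × √n, df n − 1):

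- n = 6: 0.7 × √6 = 1.71, power about 13%.
- n = 20: 0.7 × √20 = 3.13, power 68.5%.
- n = 25: 0.7 × √25 = 3.50, power 81%. This is the smallest n that reaches 80%.

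The figure of 6 does not reproduce. A one-sided test needs 21 and the normal approximation 22. Twenty falls short of 80% power on the plan's own inputs.

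**3. Power for a closed arm and a completed arm** (d = 0.7, two-sided alpha 0.016). Against saline the noncentrality is d × √(n₁n₂/(n₁+n₂)), df n₁ + n₂ − 2.

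| Comparison | Noncentrality | Power |
|---|---|---|
| Paired, n = 20 | 3.13 | 68.5% |
| Paired, n = 80 | 6.26 | >99.9% |
| Rinse v saline, 20 v 20 | 0.7 × √10 = 2.21 | 39.0% |
| Rinse v saline, 20 v 80 | 0.7 × √16 = 2.80 | 63.7% |
| Rinse v saline, 80 v 80 | 0.7 × √40 = 4.43 | 97.6% |

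The smallest d detectable with 80% power is 0.79 paired and 1.07 against saline at 20 per arm, compared with 0.37 and 0.52 at 80.

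**4. Precision.** The documents give no SD, so a log10 SD of 0.5 to 1.5 is assumed. The 95% half-width is t(0.975, n₁+n₂−2) × SD × √(1/n₁ + 1/n₂).

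| Patients | t × √(1/n₁ + 1/n₂) | SD 0.5 | SD 1.0 | SD 1.5 |
|---|---|---|---|---|
| 20 v 20 | 2.024 × 0.316 | 0.32 | 0.64 | 0.96 |
| 20 v 80 | 1.984 × 0.250 | 0.25 | 0.50 | 0.74 |
| 80 v 80 | 1.975 × 0.158 | 0.16 | 0.31 | 0.47 |

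At SD 1.0 these are factors of about 4.4, 3.1 and 2.0. The 20 v 80 row assumes that saline continues to 80 and that all of it is used, including saline patients enrolled after the arm closed.

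**5. A very large effect.** The hypothesised reduction of more than 95% is −log10(0.05) = 1.30 log10. Taking 1.30 as the effect in each comparison and assuming an SD of log10 change from 1 to 2, power at n = 20 runs from 99.8% down to 61% paired, and from 94% down to 33% against 20 saline patients (alpha 0.016).

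**6. Chance of missing infectivity activity.** Suppose that ineffective means a non-significant paired test at one time point; the plan does not say. A rinse with a true infectivity effect of d = 0.7 is then missed 1 − 0.685 = 31.5% of the time at n = 20.

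**The case against.** The best defence is that infectivity is what the trial cares about. The title speaks of inactivation, the rationale is to make saliva less infectious, the sample size cites infectivity studies, and section 9.1 says the sampling interval was chosen to see when infectivity rebounds. A rinse that leaves infectivity unchanged fails that purpose, and nothing in the plan shows how often RNA or antigen would fall without infectivity. This makes infectivity a reasonable component of the rule. It does not override the plan's own ranking, and section 9.4 does not say that the ranking was set aside deliberately.

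A second defence is that 80 per arm was derived from the 60-minute comparisons, so it is not the number needed for the 30-minute hypothesis. That is fair. However, the 30-minute figure of 6 does not reproduce, and 20 is below the 25 that the stated inputs require.

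A reader might also infer four stronger points that the documents do not support:

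- **That the whole study can be stopped on infectivity alone.** The whole-study rule says antiviral effects and names no outcome. Section 1.1 assesses viral load by RNA and antigen, so the term could include them. It is true that if every active arm failed on infectivity, the arm rule alone would end their enrolment.
- **That the primary question would go unanswered.** The closed arm's samples remain and can be assayed. At 20 v 20 every half-width in step 4 is below 1.30, so an observed difference of that size would exclude no effect at each SD shown. The accurate word is underpowered.
- **That an arm ends at exactly 20.** Assays take weeks to months and no enrolment pause is stated, so an arm may be larger when it closes.
- **That the standard error always doubles.** It doubles within the arm and at 20 v 20, but rises less at 20 v 80. The plan's ANCOVA could also change the precision.

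**Conclusion.** The point holds for the arm-dropping rule. As written, that rule rests on a tertiary outcome alone, so a rinse active on RNA or antigen can be closed at about a quarter of its planned size. At d = 0.7 this takes power from above 99.9% to about 68% paired, and from 98% to 39% against saline at 20 v 20. A very large effect with low variability could still be detected.

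The power figures rest on the plan's effect size and alpha and on 20 patients at closure. The interval widths rest on assumed SDs. How often such a closure would occur cannot be estimated, because the plan defines no test for ineffective and gives no relation between infectivity and the primary outcomes. For the whole-study rule the defect is an undefined term. Section 9.4 should be changed before the interim analysis, since enrolment lost in a closed arm is hard to recover.

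**What to change.** Reword section 9.4 as follows:

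- An active rinse arm is discontinued for lack of efficacy only if it shows no effect at 15 and 30 minutes on the primary outcome(s) available at the interim as well as on infectivity. The primary outcome is RNA, or antigen if qRT-PCR is unsuccessful, as section 9.5 allows.
- Define antiviral effects in the whole-study rule on the same outcomes.
- State the test, threshold and alpha for no effect; without them neither rule can be applied. In choosing the infectivity threshold, reconcile the more than 50% in section 9.1 with the more than 95% in sections 1.2 and 9.5.2.
- Run the planned RNA or antigen assays on the first 120 patients as one batch with the infectivity assay.

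Saying active arm also makes clear that the saline control is not subject to the rule; section 9.4 does not exempt it at present.

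The cost is protocol wording and doing planned assays earlier. Fewer arms may be dropped, so less enrolment is saved. The assays are split into an interim and a later batch, which sits against the wish in section 9.5 to run large batches; with 20 patients per rinse in the interim batch, the rinses stay balanced within it. Total enrolment stays within 480. If the sponsor prefers to keep infectivity as the sole criterion, section 9.4 should give the reason and reconcile it with the ranking in section 9.5.
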